After the baseline assessment, infants in the START-Play group will begin the intervention *with therapists from the START-Play project trained specifically in the START-Play intervention*, and the infants in the control group will continue with their regular services *with their community service provider*. All infants will receive the same assessments, as well as survey instruments to the families to determine the level of other services received by the infant. All infants will have regular intervention sessions videotaped at least once for quantification of procedures and to assure the fidelity of the intervention being provided across children.

The control intervention is the usual Early Intervention services provided to infants and mandated by public law, which consists of general developmental education and advice and in some cases low frequency therapy. Infants randomized to the intervention group will receive home visits twice weekly for the START-Play physical therapy intervention for three months. *The daily intervention will be provided by the caregiver, based on suggestions from the twice weekly visits of the START-Play therapist*. The START-Play Intervention is designed to advance sitting and reaching, and secondarily improve exploration, manipulation and problem-solving skills. *The START-Play therapy visits will be provided by either the primary investigator or by a consultant therapist (from Children’s Hospital trained and supervised by the PI*. See appendix B in full proposal for examples of START-Play intervention activities.

4. Instruments

1) Primary Measures for Sitting and Reaching

These variables quantify the initial functional delays in these skills and changes during the Intervention and Follow-up periods. *Data will be collected using video by a START-Play assessment therapist and the post doctoral fellow on the START-Play grant (to be hired)*. *Data reduction and coding will take place at various sites, with each site having a focus (Duquesne for kinematics, Delaware for reaching, VCU for problem solving, UW for Bayley and GMFM, UNL for fidelity and overall statistical analysis and data management*.

- GMFM sitting section

The Gross Motor Function Measure (GMFM, Russell et al 1993) is the international standard outcome assessment tool for quantifying change in the gross motor abilities of children with neuromotor disorders (inter-rater reliability, $r=.97$, Russell et al 2000).

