- Hand position at initial contact and during contact: open/closed hand, ventral/dorsal surface.

Secondary Measures: Child and Family Characteristics

Child characteristics (Severity, Cognitive, Age, Health) will be recorded, respectively, from previously described Severity Index, Bayley III scores, and a Demographic questionnaire and Health questionnaire, which are both completed by parents. Environmental factors include: 1) Parent/child interaction (PCI-DMC) See Figure 9, Appendix B., 2) Home environment (HOME scale [Elardo & Bradley, 1981]), 3) SES, 4) program attendance/participation (visit counts), and 4) overall amount of services (Therapy Services questionnaire). The Home Observation for Measurement of the Environment (HOME) Inventory – Infant/Toddler version assesses the home

environment including adult/child contact, social/cultural experiences, physical environment, and access to toys. SES will be measured on a Demographic questionnaire completed by parents. Program attendance will be recorded by the number of accomplished visits, documented by the therapist visiting the home. Amount of therapy will be recorded via the Therapy Service questionnaire completed by parents (see Appendix B).

vi. Fidelity of implementing the START-Play intervention

Our fidelity approach will determine the degree to which all elements of the START-Play intervention are delivered across treatment and control conditions (Knoche et al, 2010). We will assess dosage, adherence, quality, participant responsiveness, and program differentiation (Berkel et al., 2011; Cordray & Pion, 2006; Dane & Schneider, 1998; O'Donnell, 2008) with three primary measures: (1) START-Play Home Visit Coding Guide (adapted from the Home Visit Observation Form; McBride & Peterson, 1997) (see Appendix B); (2) Therapy Services Form (adapted from Westcott & Effgen, 2011; Appendix B); and (3) Home Activity Log (Appendix B). Both the experimental and BAU groups will be measured using these instruments. Relevant fidelity metrics for dosage, adherence and quality (or some combination) will be derived in consultation with our team from the Statistics and Research Methodology Unit of CYFS, allowing us to account for fidelity as a covariate in the analysis of treatment effects.

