Two components of fidelity are particularly relevant in our investigation. Both what the therapist does during the home visit sessions, and the intervention as carried out by the family will be measured. **Adherence** to specific features of the START-Play intervention (type of practice) and **quality** of implementation will be measured in both treatment and control groups with the START-Play Home Visit Coding Guide (Appendix B). This guide contains both adherence items (1-10) and quality items (items 11-16) to yield an adherence score and a quality of implementation score. This data will be collected via videotape by an assistant trained for data collection, and then coded in the lab by a trained and reliable observer. One session per month during the three intervention months will be observed. This measure yields a total adherence score indicating the percentage of criterion steps (percent of items 1-10 addressed during session, yes/no) implemented by the therapist, and a total quality score reflecting accuracy of implementation (average of times items 11-16 are performed to reflect a rate of implementation).

Dosage of both amount of services received (i.e., START/EI and outpatient) as well as specific tasks (amount of practice) will be recorded for both groups. An attendance log recorded by the interventionist will document number of home visits completed by both groups. This data is collected in EI programs, and should be available in the BAU group. Additional services for the infants outside of the START-Play intervention and their EI intervention (e.g., outpatient therapy) will be counted on the Therapy Services Form to quantify dosage of motor intervention.

Implementation of the intervention by families (**participant responsiveness**) will be documented at each assessment time for both groups using the Home Activity Log (see Appendix B), measuring how frequently families or caregivers implement strategies learned during the home visit sessions when therapists are not in the home. Families will briefly document how often and what type of activity suggestions are carried out in the home

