For the START-Play group, fidelity of implementation will also be maintained by using the START-Play Intervention Checklist that identifies essential criteria of the intervention (see Appendix C). At the end of each session, the interventionist will check off each objective addressed. The interventionist will record notes, and parent contributions to each session. We will video three sessions per therapist at the start of the study and the site PI will observe and code using the intervention checklist. 90% agreement between the site PI and therapist self-check is

targeted. If 90% agreement is not attained, the site PI will re-train the therapist and repeat the assessment. Upon attaining 90% match with PI in performance, one video per month will be checked by the site PI to maintain intervention fidelity. The project PI and each site PI will be available for consultation to each therapist as needed. Monthly meetings will be held via on-line video conference to assure fidelity by reviewing strategies, activities, and problems.

vii. Comparison (BAU) group

The comparison group will receive their usual early intervention without any interference. They will receive the same assessments following the same schedule as the infants in the intervention group. Although the children in the comparison group may be working on some of the same goals as the intervention group because they are at a similar point developmentally, no training or support related to the START-Play program will be provided.

Early intervention programs characteristically provide variable services to each child. Therefore, it may be that the control group receives services at least partially similar to the START-Play group. The START-Play Home Visit Coding Guide will be utilized monthly during the three-month intervention period to document and describe differences or similarities in intervention programs (**program differentiation**) between the BAU and START-Play groups. In addition, the Therapy Services Form will describe the frequency and amount of intervention received by each child, and will be used to quantify and evaluate additional services. The overall composition of both groups is expected to be equal because of the randomization process.

Anticipated differences between the START-Play intervention and the BAU intervention are summarized in the following Table 4.

Table 4. Comparison of START-Play to Business as Usual Early Intervention program

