assessed for the full potential of information. Appropriate error-rate control is discussed in a later section. Severity of neuromotor disorder (stratification variable) and fidelity of implementation will be added as covariates, and child-level characteristics, such as gender and ethnicity, also may be included in the analysis as child-level covariates. Due to the small sample size ($J = 4$) and the convenience sampling of sites involved in the study, site will be included as a *fixed* classroom level effect rather than an additional hierarchical level or random effect. Our analytic model is presented as a piecewise LMM where Y_{it} is the outcome variable score at time t for child i , TRT_{0i} is a contrast variable denoting the intervention status for child i (i.e., 0=BAU, 1=START-Play), RX_{it} is the passage of time during the intervention phase of the study from baseline to the end of the third month, and LT_{it} is the passage of time from the end of intervention through one calendar year since entering the study. While presented here as linear effects within each study phase (RX and LT), we will also explore any potential curvilinearity as well. The second line of the equation reflects the remaining fixed covariate effects ($CTRL_{0i}$ =neuromotor disorder severity, fidelity;

COV_{0i} =child covariate [i.e., gender]; and S_{0i} =site). *The model can be expanded to consider additional covariates*

$$Y_{it} = \gamma_{00} + \gamma_{01}TRT_{0i} + \gamma_{10}RX_{it} + \gamma_{20}LT_{it} + \gamma_{11}TRT_{0i}RX_{it} + \gamma_{21}TRT_{0i}LT_{it} + \gamma_{02}CTRL_{0i} + \gamma_{03}COV_{0i} + \gamma_{04}S_{0i} + u_{0i} + u_{1i}RX_{it} + u_{2i}LT_{it} + \varepsilon_{it}$$

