such as Bayley score at baseline by adding additional parameters to this portion of the model. A random intercept (u_{0i}) and random slopes ($u_{1i}RX_{it}$ and $u_{2i}LT_{it}$) will be included to capture individual differences in outcome levels at entry into the study, and change through each phase of the study (intervention and follow-up). Finally, we will include a residual term (ε_{it}). We expect that γ_{01} , the mean difference between conditions at baseline, will not differ significantly from zero, reflecting no initial group differences and an effective randomization. This parameter also serves to statistically control for any differences at baseline (significant or otherwise) that may be observed despite the random assignment to condition. The parameter, γ_{11} , as the difference between condition slopes through the end of the intervention, is expected to be significantly greater than zero, reflecting a larger rate of change in outcomes as a result of START-Play participation; and γ_{21} as the difference between condition slopes during follow-up will either be not significantly different from zero, reflecting maintenance of the net intervention effect, or significantly greater than zero, reflecting a continued improvement in outcomes due to the START-Play intervention. Estimates of effect sizes with confidence intervals will be provided.

[figure not shown]
Control of the family-wise error rate (FWER) is necessitated by the presence of multiple outcome measures as discussed in the prior **rationale for using multiple measures of developmental skills**. We define the family of tests as containing the four primary outcomes as described in the Measures section. We will control FWER by conducting the permutation step-down procedure (Westfall & Young, 1993) within a repeated measures design (Lix & Sajobi, 2010) allowing for estimation of intervention effects while controlling for correlation between outcomes due to the common theory of change construct.

Evaluation of Primary Hypotheses 3 & 4:

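### The primary model adjusts for fidelity, which is measured after randomisation: γ01 is then not the baseline difference, and infants without a score can drop out of the ITT analysis

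*SAP*

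**What the plan says.** SAP section ix (Evaluation of Primary Hypotheses 1 & 2) states that "Severity of neuromotor disorder (stratification variable) and fidelity of implementation will be added as covariates". Gender and ethnicity are optional; fidelity is not. In the printed equation it sits in CTRL as a child-level main effect with coefficient γ02, not interacted with time. Section vi gives the same intention: "allowing us to account for fidelity as a covariate in the analysis of treatment effects". The metric is still to be derived from dosage, adherence and quality.

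On timing and coverage, section vi says that adherence and quality "will be measured in both treatment and control groups with the START-Play Home Visit Coding Guide", and that "One session per month during the three intervention months will be observed". Section vii uses the same guide to document how the two programmes differ. Its Table 4 anticipates differences in frequency and content, although the text allows that "it may be that the control group receives services at least partially similar to the START-Play group".

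Section ix then describes γ01 as "the mean difference between conditions at baseline, will not differ significantly from zero, reflecting no initial group differences and an effective randomization". It also promises that "Estimates of effect sizes with confidence intervals will be provided", without saying whether these come from slopes or from adjusted levels.

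On missing data, section i (Retention) aims at intention to treat through FIML, without list-wise deletion or imputation. Section ix assigns the mixed models to SAS PROC GLIMMIX. Neither section gives a rule for an infant with no fidelity score. Section viii expects its moderators, a list that includes attendance and fidelity, not to differ between arms because of randomisation.

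**The concern.** Fidelity arises after randomisation and probably differs by arm. Three things follow.

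1. The coefficient that the SAP reads as a randomisation check becomes a contrast at equal fidelity. Arms that were equal at baseline could look unbalanced, and a real imbalance becomes harder to see. Any effect size built on adjusted levels, such as γ01 + 3γ11 at month 3, moves with it and could be too small or too large.
2. Fidelity is one value per child. If that value is missing, a complete-covariate fit loses all of that child's visits, including baseline. The software default then decides who is in the primary analysis.
3. Randomisation cannot be the reason for expecting balance in attendance or fidelity, because both arise afterwards.

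**Working it through.** **Which coefficients move.** At RX = LT = 0, with the other covariates balanced:

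baseline arm difference = γ01 + γ02 × (mean fidelity START-Play − mean fidelity BAU).

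So γ01 equals the baseline difference only if γ02 = 0 or the fidelity gap is 0; otherwise its bias is −γ02 × gap. Fidelity can be split into an arm mean and a within-arm deviation. The arm mean is absorbed by the intercept and TRT. When all infants share the same visits, the deviations are orthogonal to every other term, so γ11 and γ21 do not change. In simulated complete data the largest change in γ11 was about 4 × 10⁻¹⁵.

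**Size of the shift in γ01.** All inputs here are assumptions except the effect of 0.64, which is the SAP's detectable Bayley III difference (section iv), and the 70 per arm:
- visits at months 0, 2, 3, 6 and 12
- intercept variance 0.7, residual 0.3 (baseline SD 1), RX slope variance 0.01 or 0.03, LT slope variance 0.001
- true baseline difference 0; within-arm fidelity SD 1

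γ02 = u′cov(Y, F), with u = V⁻¹1/(1′V⁻¹1). Then u′1 = 1, and u′RX = 1.754 or 1.291 for the two slope variances.
- Correlation 0.3 with slope only: 0.3 × √0.01 × 1.754 = 0.053, or 0.3 × √0.03 × 1.291 = 0.067
- Correlation 0.1 with starting level only: 0.1 × √0.7 = 0.084
- Correlation 0.3 with starting level only: 0.3 × √0.7 = 0.251
- Mixed (−0.3 level, +0.3 slope): −0.251 + 0.053 = −0.198, or −0.251 + 0.067 = −0.184

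| Fidelity related to | Bias, gap 1 SD | 2 SD | 3 SD | γ01 significant at 2 SD gap |
|---|---|---|---|---|
| neither | 0 | 0 | 0 | 4–6% |
| slope 0.3 | −0.05 to −0.07 | −0.11 to −0.13 | −0.16 to −0.20 | 8–9% |
| level 0.1 | −0.08 | −0.17 | −0.25 | 10–11% |
| level 0.3 | −0.25 | −0.50 | −0.75 | 58–64% |
| mixed | +0.18 to +0.20 | +0.37 to +0.40 | +0.55 to +0.60 | 36–43% |

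The last column is from 800 simulated trials per setting. In them 3γ11 stayed at 0.63–0.65, with the same SE as without fidelity. At a 2 SD gap the adjusted month-3 level difference (true value 0.64) averaged 0.49–0.53 (slope 0.3), 0.13–0.14 (level 0.3) and 1.00–1.04 (mixed).

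**Precision of γ01, even without bias.** SE = √(0.167² + gap²/(140 × 1′V⁻¹1)), with 1′V⁻¹1 = 1.247 or 1.180. This gives 0.183–0.184, 0.225–0.228 and 0.282–0.287 at gaps of 1, 2 and 3 SD, against 0.167 without fidelity. The imbalance detectable with 80% power (2.8 × SE) rises from 0.47 to about 0.52, 0.64 and 0.80 SD.

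**Infants without a score.** The missing rate is not in the documents.
- The SAP's own Bayley III pair is consistent: Φ((1.960 + 0.842) × 0.43/0.64 − 1.960) = 46.9%, against the stated 48%.
- Multiplying the noncentrality by √(share kept), a loss of 5%, 10% or 20% of 152 infants takes power at d = 0.43 from 48% to 46%, 44% or 40%.
- If the infants lost have only a baseline visit (6 per arm), the SE of 3γ11 moves from 0.130 to 0.131. Losing 4, 7 or 10 of 70 BAU infants with complete outcomes moves it from 0.131 to 0.133, 0.135 or 0.136 (slope variance 0.01).
- If 5–15% of BAU infants are lost and they gain 0.3 SD less than the other BAU infants, the effect becomes 0.64 − 0.05 × 0.3 = 0.625 to 0.64 − 0.15 × 0.3 = 0.595.

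**Attendance.** Over 13 weeks at full attendance, Table 4 implies 3 to 13 BAU visits and 26 START-Play visits, or 29 to 39 if regular visits are added. The counts overlap only if START-Play attendance is at most 13/26 = 50%, or (13 − 3)/26 = 38% with regular visits counted at the monthly rate.

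**The case against.** The primary tests are the time-by-group interactions, and they are not biased by this. γ01 is a nuisance term, no decision rule depends on it, and sections viii and ix contain other baseline checks. That stands, and it limits the severity.

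The correlations ignore severity, which is already in the model and is an obvious link between starting level and fidelity. They should be read as conditional on severity. If half of a total correlation of 0.3 runs through severity (assumed to explain 20–40% of intercept variance), the shift of −0.50 becomes about −0.27 to −0.28; if all of it does, the shift is 0. The illustrations are also not calibrated to the Bayley III: 0.64 at 80% power implies an SE of 0.64/2.802 = 0.228, against 0.131–0.149 here. No size is fixed by the documents.

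Centring fidelity within arm would make the gap zero and restore the meaning of γ01. That is correct, but it leaves the missing-score problem in place.

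The promised effect sizes may well be slope-based, since the sentence follows the discussion of γ11 and γ21. The SAP does not say so.

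The Protocol (section 3) plans that "All infants will have regular intervention sessions videotaped at least once", so few scores may be missing, and omission of such records is standard software behaviour rather than something the documents state. The precision cost is small. What remains is that the SAP's general rule and its named software disagree for a missing covariate, and nothing resolves it.

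**Conclusion.** The concern holds. Fidelity is a firm covariate in the primary model, is measured after randomisation, and is likely to differ by arm. γ01 therefore does not have the meaning that section ix gives it, unless the gap or γ02 is zero. The shift may be nil or may be large in either direction: 0, −0.50 and about +0.4 baseline SD at a 2 SD gap are illustrations under assumed correlations, not estimates. γ11 and γ21 are unaffected except through loss of infants. That loss matters more as selective exclusion from ITT than as lost precision, and its extent is unknown. The balance expectation in section viii is unfounded for attendance and fidelity. For overall amount of service the text is ambiguous, and no claim is made. This should be fixed, but it does not undermine the primary slope tests.

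**What to change.** - Delete fidelity from CTRL in the primary model and align the matching sentence in section vi. Keep only variables fixed before randomisation: severity, site and baseline child covariates.
- Report fidelity and attendance in supportive analyses labelled as non-ITT, and state there how a missing score is handled.
- Limit the balance statement in section viii to pre-randomisation variables.

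The cost is SAP wording only. Fidelity and attendance are still collected and reported, the slope estimates keep their precision, and γ01 regains its stated meaning.

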- c. problem-solving Variable: IGDI problem-solving score
- d. global development Variable: Bayley III score

Hypothesis 2: Compared to the BAU group, the START-Play group will show greater sustained improvements from pre-intervention to one year since start of intervention (long-term effect) in:

- a. sitting Variable: Gross Motor Function Measure (GMFM) sitting scores
- b. reaching Variable: Number of toy contacts
- c. problem-solving Variable: IGDI problem-solving score
- d. global development Variable: Bayley III score

Hypothesis 3 (Mediation): Improvements in global development will be (at least) partially mediated by improvements in problem-solving as a function of the intervention at the end of the project (long-term proximal effect).

Variables: GMFM scores, toy contacts, IGDI problem-solving and Bayley III scores.

SECONDARY HYPOTHESES

Analysis of moderators

1. *Hypothesis:* Severity of motor impairment will have a significant influence on overall change in IGDI problem-solving, and motor scores, as well as Bayley III scores. Variable: Severity score (see Table 1)

2. *Hypothesis:* Factors external to the child (socialization opportunities [Modified Parent Child Interaction-Dyadic Mini Code scores (Censullo, 1991) (PCI-DMC)], and home environment (HOME Inventory [Bradley, 1993] & SES), will have a moderate effect on change in GMFM, problem-solving, and Bayley III scores.

Further analysis of motor variables

3. *Hypothesis:* The START-Play group will show posture control measures that are closer to normative values than the BAU group from pre to post intervention. This hypothesis tests additional variables quantifying sitting to supplement Primary Hypothesis 1. Variables: Kinematic measures taken from video analysis.

4. *Hypothesis:* Compared to the BAU group, the START-Play Intervention group will show greater improvements in duration of toy contact and object manipulation from pre to post intervention. This hypothesis tests additional variables quantifying reaching to supplement the

Primary Hypothesis 2. Variables: Unilateral and bilateral contact number and duration, and type of contact (i.e. hand open or closed; palmar or dorsal hand surface, manipulation variables).

iii. Research Design

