We propose a 3-month randomized trial with repeated measures design plus a nine-month follow-up. The design is longitudinal to best capture changes over time within both the BAU group and the START-Play group, and to distinguish advances in skill due to the specific intervention vs. general development under the usual model. Recruitment of study participants will be continuous throughout the project’s recruitment period, and assignment to condition will occur at the individual child level. It will not be possible to have a control group without intervention because all recruited children will be delayed enough to have mandated early intervention services. The experimental group will receive the START-Play intervention as well as their regular Part C services. Randomization will be stratified by the severity of neuromotor disorder (mild, moderate and severe). This stratification will help to ensure that the intervention groups are balanced. Randomization will be created using a random number generator using blocks of size 4 or 6, and arranged in sealed envelopes by our biostatistician, separately for each site. Numbered group assignment will be dated and faxed to the PI to verify the process.

A scale created in a previous US Dept. of Education NIDRR-funded study of infants with CP helps ensure equal distribution of children with varying severity of neuromotor dysfunction, and has been adapted for this study. The scale is summarized below:

Table 1. Method to Determine Severity of Disorder

Score Received on the Measure	Measures			
	Distribution	Active Movement	MACS	GMFCS
1	1 side	High	1-2	1-2
2	primarily legs	Moderate	3	3
3	all 4 extremities	Low	4	4

Scores from each column are totaled for a final score: 9-12, Severe; 6-8, Moderate; 4-5, Mild.

- Distribution refers to the areas of the body affected by neuromotor dysfunction.
- MACS: Manual Abilities Classification Scale (Hidecker et al, 2009) describes use of the hands and arms
- GMFCS: The Gross Motor Function Classification System (Palisano et al, 1997) classifies a child’s motor involvement on the basis of functional gross motor abilities.

The assessment schedule covers entry month (between 7-16 months of age) and the following 12 months (between 19-28 months of age). Assessments are at Baseline, Intervention (Rx) and Follow-up. Table 2. Assessment Schedule

Assessment number	1	2	3	4	5	6
Timetable (months after study entry)	0	1	2	3	6	12

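### Severity and site define the randomization strata but enter the primary model on the intercept only, and the permutation test is not tied to the strata: valid, possibly somewhat conservative, cheap to improve

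*SAP*

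**What the plan says.** SAP section iii stratifies randomization by severity in three levels. The allocation lists, in blocks of 4 or 6, are "arranged in sealed envelopes by our biostatistician, separately for each site". That makes up to 4 × 3 = 12 strata.

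Section ix, Primary Hypotheses 1 & 2, gives a piecewise linear mixed model. Only the treatment indicator is multiplied by the two time variables, RX (intervention phase) and LT (follow-up). On covariates it says "Severity of neuromotor disorder (stratification variable) and fidelity of implementation will be added as covariates". Site is a fixed "classroom level effect rather than an additional hierarchical level or random effect". In the equation, "The second line of the equation reflects the remaining fixed covariate effects", and none of these terms has a product with time. The expansion the SAP allows adds parameters to that same part of the model.

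The short-term effect is γ11, the treatment-by-RX slope; section iv bases the power simulations on the same parameter. For multiplicity, "We will control FWER by conducting the permutation step-down procedure" is the plan, with no statement on whether arm labels are shuffled within strata. Severity-by-time terms appear only in the secondary moderator models.

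Secondary Hypothesis 1 (section ii) reads: "Severity of motor impairment will have a significant influence on overall change in IGDI problem-solving, and motor scores, as well as Bayley III scores".

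**The concern.** A factor used to stratify allocation is normally carried into the analysis so that the test credits the balance it creates. Here it is carried in where it cannot do that. If more severely affected infants change at a different rate, severity contributes to the spread of slopes. Stratification removes most of that contribution from the arm comparison, but the model still counts it in the standard error of γ11. An unrestricted permutation makes the same mistake, because it allows shuffles with severity imbalances that the design rules out.

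The outcome with room to gain is the Bayley III, stated at 48% power for d = 0.43; the other three primary outcomes are stated at 93% to over 99%. Conservatism is also not wholly harmless for Hypothesis 2, because sections iv and ix read a non-significant γ21 as maintenance, and an over-wide standard error makes that easier to claim. I have not quantified this.

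**Working it through.** **1. Why intercept terms do nothing for γ11.** The slope part of the model contains only a constant and treatment, and both are also in the intercept part, where γ01 is free. With complete data the estimate of γ11 is then the unadjusted arm difference in change; anything constant over time for a child drops out. Generalized least-squares fits to simulated trials confirm this:
- Complete data: γ11 estimates with and without severity and site were identical (maximum difference 0.0000).
- 10% dropout: the standard error went, for example, from 0.2404 to 0.2386, a change of 0.0018/0.2404 = 0.7%.

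**2. Reproducing the stated Bayley power.** Inputs from section iv: two-sided α 0.05, N = 152, d = 0.43, power 48%, detectable d = 0.64 at 80% power. The SAP does not give all its variances, so I take the standard error from its detectable effect: 0.64/(1.960 + 0.842) = 0.2284. Power at 0.43 is Φ(0.43/0.2284 − 1.96) = 46.9%, about one point from 48%. Conversely, 48% implies a noncentrality of 1.91 and a detectable d of 0.63.

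**3. Effect of crediting severity.** Let R² be severity's share of the variance of 3-month change. The documents give no value; 5%, 10% and 20% are assumed.
- Power = Φ(1.91/√(1 − R²) − 1.96)
- Detectable d = 0.64 × √(1 − R²)
- Level of the model-based test as written = 2[1 − Φ(1.96/√(1 − R²))]
- Excess width of the standard error as written = 1/√(1 − R²) − 1

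| R² | Power | Detectable d | Level as written | SE too wide by |
|---|---|---|---|---|
| 0 | 48% | 0.64 | 5.0% | 0 |
| 5% | 50% | 0.62 | 4.4% | 2.6% |
| 10% | 52% | 0.61 | 3.9% | 5.4% |
| 20% | 57% | 0.57 | 2.8% | 12% |

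Reaching 80% needs 1 − R² = (1.91/2.802)² = 0.465, a share of about 54%.

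**4. Which shares fit the SAP's figures?** Section iv gives a slope variance of 0.05 without a time unit or scale. Here d is taken in baseline-SD units, an assumption.
- If 0.05 refers to the whole phase, a change variance of 2(0.95) + 0.05 = 1.95 with 76 per arm reproduces section iv (power 47.5%, detectable d 0.635). Severity can then explain at most 0.05/1.95 = 2.6%, a ceiling of about +1 point.
- If 0.05 is per month squared, slopes contribute 9 × 0.05 = 0.45 over three months. Matching section iv then needs a residual variance near 0.8, so slopes are 0.45/(1.6 + 0.45) = 22% of the change variance. A 10% share would need severity to explain about 45% of all slope variance; a 20% share, about 90%.

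**5. The permutation test.** Simulated change scores for 152 infants in 12 strata, 1,500 trials per row, 299 shuffles. Monte Carlo error is about 1.3 points on power, so compare within rows.

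| R² | Level, unrestricted | Level, within strata | Power, unrestricted | Power, within strata | Power, within strata and severity-adjusted |
|---|---|---|---|---|---|
| 0 | 4.7% | 5.0% | 45.9% | 47.4% | 47.1% |
| 5% | 4.7% | 4.9% | 49.9% | 51.3% | 51.5% |
| 10% | 3.7% | 4.7% | 44.7% | 48.7% | 48.7% |
| 20% | 3.1% | 5.3% | 45.8% | 55.9% | 55.1% |

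Severity adjustment with unrestricted shuffling gave 49.4% and 54.5% at shares of 10% and 20%, so either change alone delivers the gain. A separate simulation of the four-outcome step-down test (2,500 trials per cell, 10% loss, outcomes correlated 0.32 by assumption) agrees. At shares of 0/5/10/20%, Bayley power was 45/46/46/45% unrestricted, 46/48/49/54% within strata, and 46/49/50/55% with severity-by-time as well.

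**The case against.** The strongest reply is that little precision is actually being lost. Stratified allocation already balances severity: with a strong assumed severity effect on slope and complete data, adding severity × RX moved the empirical standard error only from 0.2142 to 0.2131, while the model's own standard error fell from 0.2290 to 0.2195. What is corrected is a conservative standard error, and conservatism is the safe direction. This stands. A reader might infer that the primary test is invalid or inflates type I error; the documents and the calculations do not support that.

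The SAP is also silent on the permutation scheme rather than wrong, and the simulations used change scores, not the planned mixed model. An analyst could shuffle within strata under the present text. That stands too, and is why one sentence is enough there.

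Secondary Hypothesis 1 is weaker support than its wording suggests. It sits under moderators, and section ix tests it as modification of the treatment effect. It does not clearly predict that severity explains slope variance in both arms. Severity's share is therefore an open assumption.

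Finally, the 48% is disclosed, and no plausible share brings Bayley to 80%. This limits the priority of the point but does not remove it, since the change uses only data already collected.

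**Conclusion.** The point holds as a low-priority improvement. The structural facts are in the documents: allocation stratified by severity and listed by site, both factors on the intercept only, the slope difference as the tested effect, and no stated permutation scheme. That intercept-only covariates leave γ11 essentially unchanged follows from the model: exactly with complete data, and within 1% of the standard error at 10% dropout.

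The size is not established. From 48% Bayley power the gain is nil if severity is unrelated to change, and at most about 1 point if the 0.05 slope variance refers to the whole phase. At assumed shares of 5% to 10% it is about 2 to 4 points. About 9 points needs a 20% share, which is hard to reconcile with section iv. These figures are at the unadjusted two-sided 0.05 level.

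Two stronger readings are tempting. One is that the change rescues the Bayley outcome; it does not, since a share of about 54% would be needed. The other is that the two changes add up; for the permutation test they deliver the same gain. Whether baseline testing precedes allocation (Protocol section 3 against the entry criteria in Protocol section 5 and the severity scoring in SAP section iii) is a separate matter of reconciling those passages, and nothing here depends on it.

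**What to change.** 1. In SAP section ix, state that the Westfall-Young step-down permutation shuffles arm labels within the site-by-severity randomization strata. This is worth stating whatever the gain, because it fixes the confirmatory test before data are seen.
2. Pre-specify severity × RX and severity × LT in the primary mixed model. Their main use, once item 1 is in place, is that the reported standard errors and confidence intervals also reflect the stratification.
3. Describe the expected gain as unquantified and probably small.

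Cost: one SAP sentence and about four model terms (two severity contrasts × two phases). If severity is irrelevant, the terms cost up to about 0.5 point of power (46.9% to 46.4% on the back-calculated standard error). No new data, visits or staff are needed.
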